4.2 Target Accrual and Study Duration

A maximum of 38 subjects (20 patients from Group A and 18 patients from Group B) at multiple sites, including RPCI will be enrolled. Accrual is expected to take up to 4 years. Patients will be on study for approximately 18 – 24 months.

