11 STATISTICAL METHODOLOGY

11.1 Sample Size Determination and Analysis

In a Phase II and Phase III study of single agent topotecan or single agent irinotecan as shown in **Table 1** in recurrent SCLC, the median time to progression of the arms were 2.2 - 4 months.^{6,8-12} Based on this, the primary endpoint of this trial will be the proportion of patients who are progression-free at 18 weeks. Progression-free survival was chosen as the primary endpoint, rather than response rate, as this is appropriate clinical endpoint for cytotoxic agents such as NKTR-102 and for SCLC. A single-stage design will be used to assess the primary endpoint for each patient group. A treatment success was defined as a patient who was progression-free at 18 weeks. To evaluate Group A, the largest success proportion where the proposed treatment regimen would be considered ineffective in this population is 5%, and the smallest that would warrant further subsequent studies is 25%. Twenty evaluable patients will be entered on this study. If 2 or fewer successes are observed, this regimen will be considered ineffective in this patient population. If 3 or more successes are observed, this will be considered evidence that this treatment may be recommended for further testing in subsequent studies. Assuming that the

number of successes is binomially distributed, this design controls the Type I Error to be $< 10\%$ and has 90% power to detect 25% 18-week PFS rate. To evaluate Group B, the largest success proportion where the proposed treatment regimen would be considered ineffective in this population is 10%, and the smallest that would warrant further subsequent studies is 35%. Eighteen evaluable patients will be entered on this study. If 3 or fewer successes are observed, this regimen will be considered ineffective in this patient population. If 4 or more successes are observed, this will be considered evidence that this treatment may be recommended for further testing in subsequent studies. Assuming that the number of successes is binomially distributed, this design controls the Type I Error to be $< 10\%$ and has 90% power to detect 25% 18-week PFS rate. Patients who come off study (e.g., due to toxicity) and start an off-protocol therapy prior to 18 weeks will be considered failures at that point.

The evaluable population is defined as patients who meet eligibility requirements and receive any protocol treatment. Unevaluable patients will be replaced.

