Progression-free survival is defined as the time from registration to the date of first documented disease progression or death. Survival time is defined as the time from registration to death due to any cause. Patients who loss-to-follow-up or alive at time of analysis will be censored at the last contact of known alive. The distribution of time to disease progression and survival time will be estimated in each group using the method of Kaplan–Meier. Probability of PFS at 18 weeks and 24 week and probability of survival at 3, 6, and 9 months will be estimated. All eligible and treated patients will be included in the analysis of the primary endpoint.

All adverse events, regardless of attribution, will be summarized (overall and by group).³⁴

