3. SUBJECT REGISTRATION

The subject completes the **Gender, Race, and Ethnicity Form** and this is placed in the study binder.

RPCI does not grant exceptions to eligibility criteria.

Phase 2 Protocol Registration Instructions

The **Subject Screening and Enrollment Log** must be faxed or emailed to the RPCI Network Office within 24 hours of the date the subject is consented. Once the Investigator has reviewed eligibility, complete the **Eligibility Verification Form** and **fax** to the RPCI Network Monitor at [contact] or email to [contact].

4. **STUDY DEVIATIONS**

- If a deviation has occurred to eliminate hazard, this must be reported to the RPCI Network, site IRB and any other regulatory authority involved in the trial.
- ANY study deviation will be recorded on the **Study Deviation Log**.
- Subjects inadvertently enrolled with significant deviation(s) from the study-specified criteria will be removed from the study.
- Notify the RPCI Network Office of any early subject withdrawal and appropriately document the discontinuation and the reason why.

5. **STUDY DOCUMENTATION**

- Study documents must be filled out completely and correctly. Ditto marks are not allowed.
- If an entry has been documented in error put a single line through the entry and initial and date the change. The RPCI Network Monitor must be able to read what has been deleted.
 - Do **NOT** use white-out, magic marker, scratch-outs.
 - Do **NOT** erase entries.
- Use only black ink for documentation on the accountability form and any other study forms.

6. **DRUG ACCOUNTABILITY**

Drug accountability must be strictly maintained.

- Responsibility rests solely with the Investigator but can be delegated as appropriate (e.g., to pharmacy personnel).
- A drug accountability record form (DARF) will record quantities of study drug received, dispensed to subjects and wasted, lot number, date dispensed, subject ID number and initials, quantity returned, balance remaining, manufacturer, expiration date, and the initials of the person dispensing the medication.
- Study drug supply will only be used in accordance with the IRB approved study.
- Drug accountability forms are protocol and agent specific, they are study source documents and will be used to verify compliance with the study.
- An inventory count must be performed with each transaction. Any discrepancies shall be documented and explained.
- Drug accountability forms must be stored with study related documents.

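### Section 11.1 drops and replaces dosed patients later judged ineligible without a cut-off or outcome-blind rule, so selective use would take Group B's type I error above 10%; any replacement also breaks the 38-subject maximum

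*Combined protocol and SAP*

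**What the plan says.** Section 11.1 defines who counts and what happens to the rest: "The evaluable population is defined as patients who meet eligibility requirements and receive any protocol treatment. Unevaluable patients will be replaced". Later in the same section the primary analysis set is given: "All eligible and treated patients will be included in the analysis of the primary endpoint". A patient who has been dosed but is found not to have met the criteria is therefore outside the denominator and is replaced.

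Appendix A, item 4 (Study Deviations), written for network sites, adds: "Subjects inadvertently enrolled with significant deviation(s) from the study-specified criteria will be removed from the study". It does not define which deviations are significant.

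The plan sets no date by which eligibility must be final, does not require the decision to be made without knowledge of outcome, and has no sensitivity analysis in all treated patients.

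On numbers, section 4.2 gives "A maximum of 38 subjects (20 patients from Group A and 18 patients from Group B"), and the synopsis gives the same total. Section 11.1 asks for twenty evaluable patients in Group A and, for Group B, "Eighteen evaluable patients will be entered on this study".

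**The concern.** With one arm and no blinding, whoever reviews eligibility can know whether the patient has already progressed or died. Under 11.1, a late finding of ineligibility removes that failure and brings in a new patient with a fresh chance of success. The stated type I error assumes that exclusion is unrelated to outcome, and nothing in the text secures this.

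Some criteria leave room for judgement after the fact, such as successful local therapy for CNS metastases or uncontrolled intercurrent illness (section 5.2). One case touches outcome directly. CNS metastases are an exclusion, but brain imaging is not required at baseline in asymptomatic patients (sections 5.2 and 7.8). Brain disease found early on study could be read as progression, a failure, or as pre-existing disease, hence ineligible and replaced. The protocol does not say which.

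The go rules are 3 of 20 and 4 of 18, so one patient can decide a group's result. Group B has almost no slack below its stated error limit.

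The conflict between the cap and the replacement rule is separate and needs no assumption about bias.

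**Working it through.** **Inputs, all from section 11.1 unless noted.**
- Group A: 20 evaluable patients, success at 3 or more, null rate 5%, target rate 25%.
- Group B: 18 evaluable patients; the ineffective rate "in this population is 10%, and the smallest that would warrant further subsequent studies is 35"%. The rule is "If 4 or more successes are observed, this will be considered evidence that this treatment may be recommended for further testing".
- Stated properties, in identical words for both groups: "this design controls the Type I Error to be $< 10\%$ and has 90% power to detect 25% 18-week PFS rate".
- Enrolment maximum: 38 (section 4.2).

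**1. Reproduce the stated error.** X is binomial.
- Group B: P(X ≥ 4 | 18, 0.10) = 0.0982. The claim holds, with 0.18 percentage points to spare.
- Group A: P(X ≥ 3 | 20, 0.05) = 0.0755. The claim holds.

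**2. Decision ignores outcome.** The replaced patient and the replacement have the same success probability, so Group B stays at 9.82%. A simulation of 400,000 trials gave 9.81%.

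**3. A failure is always found and replaced, a success never.** One replacement matters only when the group is one success short:
- Group B: 0.0982 + P(X = 3 | 18, 0.10) × 0.10 = 0.0982 + 0.1680 × 0.10 = 0.1150.
- Group A: 0.0755 + P(X = 2 | 20, 0.05) × 0.05 = 0.0755 + 0.1887 × 0.05 = 0.0849.

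In general, replacing k failures gives the tail for n + k patients at the same cut-off:

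| Failures replaced | Group B, P(X ≥ 4 given 18 + k, 0.10) | Group A, P(X ≥ 3 given 20 + k, 0.05) |
|---|---|---|
| 0 | 9.82% | 7.55% |
| 1 | 11.50% | 8.49% |
| 2 | 13.30% | 9.48% |
| 3 | 15.20% | 10.52% |

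**4. A milder form of selection.** Suppose one particular Group B patient is truly ineligible, but this is declared only if that patient fails. The slot's success probability becomes 0.10 + 0.90 × 0.10 = 0.19. The error is P(X ≥ 4 | 17, 0.10) + 0.19 × P(X = 3 | 17, 0.10) = 0.0826 + 0.19 × 0.1556 = 0.1122.

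**5. How much selection is needed.** If step 3 happens for one Group B failure with probability q, the error is 0.0982 + q × (0.1150 − 0.0982). It passes 10% when q exceeds about 0.107.

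**6. The cap.** 20 + 18 = 38 evaluable patients, equal to the maximum enrolled. One replacement makes 39. If the cap is kept and one patient per group is lost, with cut-offs unchanged:
- Group A at 25%: P(X ≥ 3 | 19, 0.25) = 88.9%, down from 90.9%, against a stated 90%.
- Group B at its design alternative of 35%: P(X ≥ 4 | 17, 0.35) = 89.7%, down from 92.2%.

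The text states Group B's 90% power at 25%, not 35%. At 25% the power is P(X ≥ 4 | 18, 0.25) = 69.4% even with all 18 patients, so the 89.7% cannot be set against the sentence as written.

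**The case against.** The strongest reply is that replacing a patient who happens to have failed does no harm in itself. At a 10% success rate about nine patients in ten are failures, so most patients replaced for honest reasons will be failures too. Inflation needs selection: a failure declared ineligible where a success would have been kept. This is right, and step 2 shows it. A reader might infer that any replaced failure takes Group B above 10%; the figures do not support that.

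Second, eligibility is documented before dosing. The investigator signs a verification form covering every criterion, network sites send it to the monitor, and Appendix A, item 3, allows no exceptions. Concomitant drugs must be captured on the case report form (section 7.3.7), so prior CYP3A4 exposure is largely a matter of record. These steps should make late findings rare, and the documents describe no process for re-judging eligibility. But neither do they bar a late reversal, and 11.1 says what follows from one.

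Third, a reader might infer from Appendix A that dosed patients who are removed vanish from the safety and survival data. The documents do not say so. Only the primary endpoint is restricted to eligible patients. The adverse event summaries (sections 11.1 and 11.6), the reporting rules (9.1.3, 9.2.2) and survival follow-up (7.13) carry no eligibility filter. The phrase in Appendix A is ambiguous, which calls for clarification and no more.

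Fourth, the power losses in step 6 are small. That is so; what matters there is that the two instructions cannot both be followed.

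**Conclusion.** The point holds in conditional form. Section 11.1 permits outcome-dependent exclusion and replacement of dosed patients and has no safeguard against it. If ineligibility is declared selectively for failures, one such patient takes Group B from 9.82% to 11.2% (one given patient, replaced only on failing) or 11.5% (a failure always found and replaced), against a stated limit of 10%. Group A stays below 10% with one or two and reaches 10.5% with the third. With decisions that ignore outcome, both stated error rates stand. Nothing in the documents suggests that selective exclusion is intended; the gap is that nothing prevents it or would reveal it.

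The conflict between the 38-subject maximum and the replacement rule is certain and rests on no assumption. Both matters should be corrected; neither invalidates the design.

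**What to change.** - **Section 11.1, replacement.** Replace only patients who never receive study drug, or whose ineligibility is established from pre-dose records and documented before any post-dose outcome: scan, clinical progression, symptomatic deterioration, treatment discontinuation or death, whichever is first. After that, a dosed patient stays in the primary denominator. A cut-off at the first scan alone would not do. Scheduled scans begin only after Cycle 2 (section 7.11), and patients who die or deteriorate before then would remain replaceable with their outcome known.
- **Section 11.1, sensitivity analysis.** Add 18-week PFS in all treated patients, by group.
- **Section 4.2 and synopsis.** State 38 evaluable subjects (20 + 18) plus replacements as defined in 11.1, with a numerical enrolment ceiling.
- **Appendix A, item 4.** State that dosed patients removed for eligibility deviations remain in adverse event, progression and survival follow-up.
- **Group B power sentence (11.1).** Reconcile the 25% with the 35% design alternative when the section is edited.

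The cost is protocol wording and a prompt eligibility check after first dose. The downside is that an occasional ineligible patient found late stays in the denominator, which makes the estimate slightly less clean.

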Objectives	
Primary Objective:
 
 To evaluate the 18-week progression free survival (PFS) rate of relapsed SCLC patients treated with NKTR-102. 
Secondary Objectives:
 
 To evaluate the objective response rate. To evaluate the duration of response. To evaluate the overall survival. To evaluate the toxicity of NKTR-102 in this patient population. 
Correlative Objective:
 
 To explore the correlation between UGT1A1 polymorphisms and NKTR-102 toxicities.
Study Design	This is a single stage Phase II study of relapsed small cell lung cancer patients who have received only one prior systemic therapy regimen. There will be 2 patient cohorts: those progressing on first-line therapy < 3 months after completion of treatment (Group A: chemo resistant) and those progressing on first-line therapy ≥ 3 months after completion of treatment (Group B: chemo sensitive). Etirinotecan pegol will be administered at 145 mg/m ² IV once every 3 weeks. Cycles will be repeated every 21 days (± 3 days) until disease progression. Patients who develop metastases in the central nervous system (CNS) as the only site of disease progression could receive therapeutic whole brain radiation therapy (WBRT), or gamma knife radiosurgery and after completion of WBRT continue on NKTR-102. Imaging studies are scheduled to be obtained after every other 21-day cycle.
Target Accrual and Study Duration	This study will accrue a total of 38 patients over approximately 3 years (Group A; 20 patients, Group B; 18 patients). Patients will be on study for approximately 18 – 24 months.
Study Procedures	
Adverse Events: From time of Cycle 1 Day 1 until 30 days after receiving last dose of study drug.
 
Hematology: ≤ 14 days prior to initiation of study drug, Cycle 1 (Day 1 and weekly), and prior to treatment on Day 1 of subsequent cycles, 30-Day Follow-Up.
 
Chemistry: ≤ 14 days prior to initiation of study drug, Cycle 1 (Day 1 and weekly), prior to treatment on Day 1 of subsequent cycles, 30-Day Follow-Up.
 
Physical Examination (including vital signs, body weight, and height):

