7.13 Survival Follow-up

- Patients will also be followed for survival every 3 months following the 30 day follow-up visit. Survival follow-up assessments may be collected via telephone.

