- 7 Tumor assessment must be performed at least every other cycle after completing Cycle 2. Tumor assessment may be performed ± 3 days prior to treatment on Day 1 of subsequent cycles. Tumor assessment should be performed at any time during the treatment cycle that disease progression is clinically suspected so that patient can go off treatment and receive other therapy. If PET-CT was used at baseline, CT only may be used for subsequent cycles.
- 8 Brain imaging is required in symptomatic patients to rule out brain metastases, but is not required in asymptomatic patients.
- 9 Women of childbearing potential only. Must be done ≤ 7 days prior to initiation of study drug.
- 10 Hematology (i.e., complete blood count (CBC) with automated differentials or the physician discretion; WBC, RBC, HGB, HCT, platelet, MCV, MCH, MCHC, %neutrophils, absolute neutrophils, %lymphocytes, absolute lymphocytes, %monocytes, absolute monocytes, %eosinophils, absolute eosinophils, %basophils, absolute basophils, %Large Unspecified Cells (LUC), %lymphocyte total, absolute lymphocyte total, platelet confirmation, and differential confirmation).
- 11 Chemistry (i.e., complete metabolic panel (CMP): chloride, CO₂, potassium, sodium, BUN, glucose, calcium, creatinine, total protein, albumin, total bilirubin, alkaline phosphatase, AST, ALT, A/G ratio, BUN/creatinine ratio, osmol (Calc), anion gap).
- 12 Pharmacogenetic blood sample collection will be obtained at Day 1 of Cycle 1.
- 13 The patient will be asked to lie down and rest for about 10 minutes before this procedure.
- 14 Prior to Cycle 2 and Cycle 3, if clinically indicated.
- 15 Survival follow-up assessments may be collected via telephone.

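### Section 11.1 gives one censoring date, last contact known alive, for both progression and survival; PFS needs its own date, and unscanned early stoppers need a stated non-success rule.

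*Combined protocol and SAP*

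**What the plan says.** Section 11.1 dates PFS from registration to first documented progression or death, and survival from registration to death. One censoring sentence follows: "Patients who loss-to-follow-up or alive at time of analysis will be censored at the last contact of known alive". The next begins: "The distribution of time to disease progression and survival time will be estimated in each group using the method of" Kaplan–Meier. PFS is to be reported at 18 and 24 weeks.

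For the primary endpoint, Section 11.1 says: "A treatment success was defined as a patient who was progression-free at 18 weeks". It has one explicit rule for early stoppers: "Patients who come off study (e.g., due to toxicity) and start an off-protocol therapy prior to 18 weeks will be considered failures". On the denominator it says: "All eligible and treated patients will be included in the analysis of the primary endpoint". Eligible patients who received any treatment are evaluable, and only unevaluable patients are replaced.

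On scans, Table 4 footnote 7 (Section 7.14) says: "Tumor assessment must be performed at least every other cycle after completing Cycle 2". Table 4 marks no tumour assessment at the 30-day visit or in survival follow-up. Survival contact is every 3 months (Section 7.13), and "Survival follow-up assessments may be collected via telephone".

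The synopsis counts the 18 weeks from receipt of study drug, not from registration, and its sentence on 18-week PFS does not mention death.

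**The concern.** Last contact known alive is a sound censoring date for survival, because a telephone call can establish that a patient is alive. It cannot establish that the tumour has not grown. Under this schedule a patient who stops treatment without documented progression may have no further scan, yet be contacted months later. Censoring that patient's PFS at the contact date leaves the patient in the progression risk set at times when no progression could have been recorded. The denominators are then too large and the curve too high.

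For the binary endpoint, most early stoppers are already settled. Progression and death are PFS events. Off-protocol therapy is a failure. Symptomatic deterioration is reported as progression (Section 8.4), and so is a need for radiotherapy (Section 7.3.5, with CNS-only progression treated separately in Section 7.4). What remains is an evaluable patient who stops before week 18, for example for toxicity or by withdrawal, and is alive with none of these and no later scan. That patient stays in the denominator, and no sentence says how to score the case. With cut-offs of 3 of 20 and 4 of 18, one patient can decide a group's result.

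**Working it through.** **1. The plan's own figures.** Inputs from Section 11.1: Group A n = 20, at least 3 successes, null 5%, target 25%; Group B n = 18, at least 4 successes, null 10%, target 35%. With X binomial:

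- Group A: P(X ≥ 3 | 20, 0.05) = 0.0755; P(X ≥ 3 | 20, 0.25) = 0.9087.
- Group B: P(X ≥ 4 | 18, 0.10) = 0.0982; P(X ≥ 4 | 18, 0.35) = 0.9217.

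This agrees with type I error below 10% and about 90% power. The Group B power sentence prints 25%; I use that group's stated target of 35%. The misprint is a separate matter.

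**2. Kaplan-Meier, constructed example.** These counts are mine, not the protocol's. Of 20 patients, 10 progress at week 6, 5 at week 12 and 2 at week 18; 2 are scanned without progression at week 18; 1 is progression-free at week 6, is never scanned again, and is telephoned alive at week 24.

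| PFS censoring date | Week 6 | Week 12 | Week 18 | 18-week PFS |
|---|---|---|---|---|
| Last known alive | 10/20 | 5/10 | 3/5 | 0.150 |
| Last scan | 10/20 | 4/9 | 2/4 | 0.111 |

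One patient moves the estimate by 3.9 points.

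**3. Kaplan-Meier, simulation.** Assumptions: exponential progression, scans at weeks 6, 12 and 18, 10% of patients stopping scans at a uniform time before week 18, and all of them known alive beyond it (200,000 patients).

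| True 18-week PFS | Last known alive | Last scan |
|---|---|---|
| 5% | 9.5% | 5.0% |
| 10% | 14.6% | 10.1% |
| 25% | 29.3% | 25.0% |
| 35% | 38.7% | 34.9% |

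With 5% to 20% stopping scans, the upward bias is about 2 to 9 points.

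**4. Binary endpoint, one unscanned early stopper scored as a non-success.** The other n − 1 patients must supply all the successes.

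- Group A: type I error P(X ≥ 3 | 19, 0.05) = 0.0665; power P(X ≥ 3 | 19, 0.25) = 0.8887.
- Group B: type I error P(X ≥ 4 | 17, 0.10) = 0.0826; power P(X ≥ 4 | 17, 0.35) = 0.8972.

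**5. The same patient scored as a success.** The others need one success fewer: Group A P(X ≥ 2 | 19, 0.05) = 0.2453; Group B P(X ≥ 3 | 17, 0.10) = 0.2382.

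**6. Scan dates.** Week 18 is day 126. The synopsis says: "Cycles will be repeated every 21 days (± 3 days) until disease progression". On constant cycles of 18, 19, 20, 21, 22, 23 or 24 days, the first every-other-cycle scan at or after day 126 falls on day 144, 152, 160, 126, 132, 138 or 144. A rule for missing scans must therefore not turn progression first seen at such a late scan into a failure. As an extreme, suppose PFS is exponential, every patient is assessed at day 144, and progression seen then counts as failure. The success rates become 0.25^(144/126) = 0.205 and 0.35^(144/126) = 0.301, and power falls to 80.9% (A) and 83.8% (B).

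**The case against.** The censoring sentence directly follows the survival definition and speaks of being known alive, so it may be meant for survival only. That is a fair reading, but PFS then has no censoring rule, and the same amendment is needed. It is also fair that the Kaplan-Meier estimates are descriptive, and that 3.9 points is small beside a standard error of about 8 points at n = 20 (√(0.15 × 0.85/20) = 0.080). However, the bias runs in one direction and costs nothing to remove.

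On the binary endpoint, the strongest reply is that the plan already answers the question: success requires being progression-free at week 18, all eligible treated patients are counted, and a patient not shown to be progression-free is therefore not a success. I accept this as the natural reading. What stands is that it is not written down, while the PFS definition turns on documented progression and the synopsis on disease that has not progressed, which leaves room for argument once outcomes are known.

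A reader might infer from step 5 that the real type I error is about 24%. The documents do not support that. The figure requires crediting a success to a patient with no week-18 assessment, and it is conditional on such a patient existing, whereas the plan's 10% limit is unconditional.

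**Conclusion.** The main point holds. Used for PFS, the single censoring date biases the reported 18- and 24-week estimates upward; read as survival-only, it leaves PFS without a date. The sizes (15.0% against 11.1%, or about 2 to 9 points in the simulation) rest on assumed numbers of unscanned patients, since the documents give none. A reader might infer that this undermines the decision on each group. It does not, because that decision rests on a binomial count and not on the Kaplan-Meier curve.

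The secondary point is a narrow omission. On the natural reading, one such patient gives type I error of 6.7% (A) and 8.3% (B), so the stated limit holds at a small cost in power. The time-origin difference between Section 11.1 and the synopsis is minor. All of this should be fixed, and none of it invalidates the design.

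**What to change.** Amend Section 11.1 as follows:

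1. Keep last contact known alive for survival. Censor PFS at the last adequate tumour assessment.
2. State that an evaluable patient with no earlier event and no tumour assessment at or after week 18 (less the 3 days in Table 4 footnote 7) counts as a non-success.
3. State that progression is dated by first documentation, as the PFS definition already has it, so that progression first documented after day 126 is not made a failure.
4. Use one time origin, registration or first dose, in Section 11.1 and the synopsis, and mention death in the synopsis sentence.

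The cost is wording only; sample size, cut-offs and visits are unchanged. A stable but unscanned patient will count against the drug. With one such patient, power falls from 90.9% to 88.9% (A, at 25%) and from 92.2% to 89.7% (B, at 35%). With two it would be 86.5% and 86.6%. Item 3 retains a feature of the present definition: success depends partly on scan timing. On 24-day cycles, for example, scans fall on days 48, 96 and 144, so growth between days 96 and 126 that is first seen at the day-144 scan still counts as a success.
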